9.4 Whole body probe measurements (Cohort 1)

Patients in Cohort 1 will undergo whole body dose measurement using a NaI probe placed at ~3 meters from the patient. These measurements will be performed the day of injection of ⁸⁹Zr-DFO-MSTP2109A before voiding and after first void, and at each time the patient returns for imaging (typically less than 5 minutes).

9.5 Assessment for Toxicity

Safety Outcome Measures (CTCAE v4)

Infusion Reaction

Patients will be monitored during and after ⁸⁹Zr-DFO-MSTP2109A infusion for 90 minutes after the infusion. Patients who experience infusion-related symptoms should be managed as directed in Table 1.

The safety and tolerability of ⁸⁹Zr-DFO-MSTP2109A will be assessed using the following primary safety outcome measure:

- Incidence, nature, and severity of adverse events up to 1 week following antibody administration.
- Change in vital signs during administration

Table 1
 Management of Infusion-Related Symptoms

Infusion-Related Symptoms	Guidance
Grade 1	
 • Slow or hold infusion • Give supportive treatment • Upon symptom resolution, may resume infusion rate escalation at the investigator's discretion
Grade 2	
 • Slow or hold infusion • Give supportive treatment • Upon symptom resolution, may resume infusion-rate escalation at the investigator's discretion
Grade 3 or Grade 4	
 • Discontinue infusion • Give supportive treatment 
Patient may be imaged if sufficient tracer has been administered and the patient is stable, at the discretion of the administering investigator.

Given that this is a humanized antibody and the antibody will be administered only once under this protocol the likelihood of development of human anti human antibody is low. Patients enrolled, who are being treated with the ADC under protocol 11-016 will be monitored for the presence of anti-ADC antibodies as is currently stated in that study. Thus the presence, if any, of anti MSTP2109A, that would potentially interfere with ADC targeting will be evaluated in those patient on protocol 11-016. Baseline serum and 4-6 wk post infusion serum (serum separator or red top tube) will be collected and banked for future determination of HAHA response as requested by the FDA ([name] lab, storage approximately -70°C).

10.0 EVALUATION DURING TREATMENT/INTERVENTION

Laboratory Safety Assessments

Blood testing:

Hematology and blood chemistry assessments (CBC, PSA, serum BUN, creatinine, AST, ALT, total bilirubin, alkaline phosphatase, albumin, blood glucose levels, and serum testosterone level) will be done at the time points described in Table 2. Additional blood tests may also be performed at the discretion of the investigator for the purposes of planning treatment administration, dose modification, or investigation and follow-up of adverse events. These additional tests will not be documented in the CRF.

Serum samples collected from baseline and 4-6 weeks after administration of DFO-MSTP2109A will be stored to assay for immune response to ⁸⁹Zr-DFO-MSTP2109A (assay to be developed). This assay may be done in house or shipped to Genentech for processing.

Physical examination:

A physical examination including, but not limited to, general appearance, skin, neck, eyes, ears,

MEMORIAL SLOAN-KETTERING CANCER CENTER IRB PROTOCOL

IRB#:12-178 A(3)

throat, lungs, heart, abdomen, lymph nodes, extremities, and nervous system will be performed. The physical examination will include examination of known and suspected sites of disease. Physical examination results, height and weight will be recorded at baseline .

Performance Status

Performance status will be assessed using the Karnofsky Performance Status scale (Appendix A).

Vital Signs

Blood pressure and heart rate will be obtained at the time points outlined in the flowchart.

Table 2
Schedule of Assessments

Cohort 1 (A and B):

	Screening ^a		Day 1	Day 2	Days 3-5	Days 6-8	4-6 wks post dose
	Within 4 weeks	Within 14 days					
Informed consent	X						
Demographics	X						
Medical history	X						
Concomitant medications	X						
Physical exam	X						
Performance status	X						
Vital signs^b	X		X	X	X	X	
Laboratory studies^c		X					X
Serum sample for banking		X					X
Radiographic studies^d	X						
IHC for STEAP^e	Prior to enrollment						
⁸⁹Zr-DFO-MSTP2109A tracer administration			X				

MEMORIAL SLOAN-KETTERING CANCER CENTER
 IRB PROTOCOL

IRB#:12-178 A(3)

Adverse events on day of imaging			X	X	X	X	
Serial whole-body scans (Cohort 1A and 1B)^f			X	X	X	X	
Serial whole-body probe^g			X	X	X	X	
Serial blood samples^h(Cohort 1A and 1B)			X	X	X	X	

^a Screening evaluation should be performed following informed consent and within 4 weeks before study entry, except when noted otherwise. Evaluations performed as standard of care before informed consent but within the 4-week window need not be repeated.

^b Vital signs will be monitored prior to infusion and every 30 minutes for at least 2 h or later if the patient is still in the department for imaging.

^c Within 14 days laboratory studies include CBC, PSA, serum BUN, creatinine, AST, ALT, total bilirubin, alkaline phosphatase, albumin, blood glucose levels, and serum testosterone level. All laboratory studies are to be performed up to 2 weeks before study entry (serum testosterone level may be up to 4 weeks before study entry). At Days 6 to 8 CBC and comprehensive labs will be obtained.

^d Radiographic evaluations include bone scintigraphy, CT of chest, abdomen and pelvis (MRI is acceptable if CT is clinically contraindicated), and modified MRI of the pelvis, if clinically indicated. All radiographic studies are to be performed within 4 weeks before, or up to 2 weeks after study entry, provided the patient has not received treatment.

^e sample sent out to Genentech

^f Following injection with the ⁸⁹Zr-DFO-MSTP2109A tracer, the patients enrolled in the study (Patients Cohort 1 A and or 1B) will have serial whole-body PET-CT scans (WBS) performed to determine the biodistribution of the tracer. PET scans will be acquired: 1–4 hours following injection of the tracer, ~24 h \pm 8 h post-injection, ~48–96 hours post injection, and ~120–168 hours post injection. Slight variations in times due to scheduling or technical difficulties will not be considered violations

^g Whole body counts (WBC) using a probe will be performed during the imaging in the first 12 patients and the exact time recorded:

- Within 0.1 to four hours following injection of tracer on Day 1 (prior to voiding) and post voiding
- 24 \pm 8 hours post-injection (Day 2)
- ~48–96 hours post-injection (once during Days 3–5)
- ~120–168 hours post injection (once during Days 6–8)

^h For the first 12 patients enrolled, serial blood samples will be obtained for biodistribution, metabolite analysis of the ⁸⁹Zr-DFO-MSTP2109A compound will be performed on selected samples. Samples will be obtained just prior to injection of the ⁸⁹Zr-DFO-MSTP2109A tracer, and at 5 \pm 2 minutes, 15 \pm 5, 30 \pm 9, 60 \pm 19 minutes, and 120 – 240 minutes after the injection of the tracer on 24 \pm 8, and at the time of each subsequent day of imaging , ~48-96, ~120-168, slight variations in times due to scheduling or technical difficulties will not be considered violations.

Cohort 2:

	Screening ^a		Day 1	Day TBD	Follow up	
	Within 4 weeks	Within 14 days			~1 weeks post dose (Day 6-8)	4-6 weeks post dose
Informed consent	X					
Demographics	X					
Medical history	X					
Concomitant medications	X					
Physical exam	X					
Performance status	X					
Vital signs^b	X		X	X		
Laboratory studies^c		X		X		
Serum sample for banking		X				X
Radiographic studies^d	X					

⁸⁹ Zr-DFO-MSTP2109A tracer administration		X				
Adverse events		X	X	X		
Phone assessment^e				X	X	

- a Screening evaluation should be performed following informed consent and within 4 weeks before study entry, except when noted otherwise. Evaluations performed as standard of care before informed consent but within the 4-week window need not be repeated.
- b Vital signs will be monitored prior to infusion and every 30 minutes for at least 2 h or later if the patient is still in the department for imaging.
- c Laboratory studies include CBC, PSA, serum BUN, creatinine, AST, ALT, total bilirubin, alkaline phosphatase, albumin, blood glucose levels, and serum testosterone level. All laboratory studies are to be performed up to 2 weeks before study entry (serum testosterone level may be up to 4 weeks before study entry). Second set of laboratory on TBD will consist of CBC and comprehensive. At TBD CBC and comprehensive will be repeated.
- d Radiographic evaluations include bone scintigraphy, CT of chest, abdomen and pelvis (MRI is acceptable if CT is clinically contraindicated), and modified MRI of the pelvis, if clinically indicated. All radiographic studies are to be performed within 4 weeks before, or up to 2 weeks after study entry, provided the patient has not received treatment.
- e A phone call will be used to assess for changes in concomitant medications and any adverse events after all scans have been completed if the scanning time is less than 6-8 days.
- f For the 13th through 27th patients enrolled, only 1 PET scan will be performed, at a time point to be determined based on data from the first 12 patients.

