Antibody imaging will be considered feasible if 75% of the patients are antibody-imaging-positive as defined above..We will enroll 6 patients (cohort 1A) at the 10mg dose level for an initial decision on feasibility. If 4 or more of these patients have 20% or more of their active lesions detectable by ^{89}Zr -DFO-MSTP2109A then we will consider the agent feasible for imaging, otherwise we will proceed to cohort 1B. If the true feasibility rate is 40%, this rule will affords more than 82% chance that cohort 1B will be opened for enrollment; this probability is less than 17% if the true feasibility is 75%. We will also require that none of these patients experience dose severe toxicity attributable to the initial 10 mg dose before cohort 1B is opened for enrollment.

If severe adverse effect (grade 3 or 4 CTCAE) is observed in any cohort we will review with MSKCC-DSMC and IRB before continuing with accrual. If 3 patients in cohort 1A do not show acceptable imaging, as described above, we will proceed to cohort 1B.

In cohort 1B, 6 more patients will be enrolled at a higher dose (20mg) for safety and pharmacokinetic evaluation. Serial blood draws will be used to estimate the pharmacokinetic profile of the 10 and 20mg ^{89}Zr -DFO-MSTP2109A in this patient population. Pharmacokinetic analysis will be performed using a non-compartmental analysis; standard parameters such as AUC, clearance, volume of distribution, and Co will be reported. Descriptive statistics will be tabulated. If 3 patients in Cohort 1B have antibody negative imaging accrual will stop. If 4 patients in cohort 1B have positive imaging we will move to cohort 2 using the best imaging dose from cohort IA or 1B..

Based on pharmacokinetic analysis from cohorts 1A and 1B an optimal time point (based visually on optimal image quality for tumor detection and clinically/logistically feasible) will be determined for imaging and cohort 2 will enroll up to 15 patients at the dose also determined from cohorts 1A or 1B. These patients will undergo a single whole-body scan at the optimal time point. The ability of ^{89}Zr -DFO-MSTP2109A to detect tumors will be estimated from this cohort using the proportion of antibody-imaging-positive patients (within +/-22% if the true detection rate is 75%).

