This study does not intend to find the maximal tolerated dose of DFO-MSTP2109A. This is a diagnostic agent that is expected to have low incidence of adverse events. Patients will be monitored closely looking for evidence of adverse events. Because patients will likely start new therapies within 2 weeks of receiving ^{89}Zr -DFO-MSTP2109A only short term toxicity will be evaluated. The safety and tolerability of ^{89}Zr -DFO-MSTP2109A will be assessed using the following primary safety outcome measures: Incidence and nature of incidence, nature, and severity of adverse events; and change in vital signs and clinical laboratory results. Incidence and

MEMORIAL SLOAN-KETTERING CANCER CENTER IRB PROTOCOL

IRB#:12-178 A(3)

severity of adverse events will be summarized with descriptive statistics.

Dosimetry: SUVmax/mean (that can easily be converted to %ID/g) in normal organs of patients from Cohort 1A and Cohort 1B will be determined and this data over time will be used to determine the residence time in each visualized organ (liver, spleen, kidney and lung), other organ will be evaluated if clinically appropriate. The median residence time value will be used in OLINDA software to calculate the dosimetry.

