17.3.3 Attributing Causality

The investigator will evaluate the potential relationship between all clinical AEs, abnormal laboratory values, and the ^{89}Zr -DFO-MSTP2109A, and categorize the relationship according to the descriptions in Table 5. Abnormal laboratory values of clinical significance that were present at baseline and did not change in either severity or frequency during the experimental therapy or intervention and/or that can obviously be attributed to the underlying disease will be evaluated by the investigator and recorded in the “unrelated” category.

Table 6. Relationship of Adverse Event to ^{89}Zr -DFO-MSTP2109A

Relationship	Description
Unrelated	AE is clearly not related to the ^{89}Zr -DFO-MSTP2109A
Unlikely	AE is unlikely related to the ^{89}Zr -DFO-MSTP2109A
Possible	AE may be related to the ^{89}Zr -DFO-MSTP2109A
Probable	AE is likely related to the ^{89}Zr -DFO-MSTP2109A
Definite	AE is clearly related to the ^{89}Zr -DFO-MSTP2109A

Adverse events will be defined graded using CTCAE V4.0.

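### Blood tests done to investigate or follow up an adverse event are kept out of the CRF, although laboratory change is listed as a primary safety outcome

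*Combined protocol and SAP*

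**What the plan says.** Under Laboratory Safety Assessments, Section 10.0 of the combined protocol and SAP says that the hematology and chemistry panel "will be done at the time points described in Table 2". It then allows further blood tests at the investigator's discretion. The listed purposes are treatment planning, "dose modification, or investigation and follow-up of adverse events". The next sentence is: "These additional tests will not be documented in the CRF". It makes no exception for abnormal results or for results prompted by an adverse event, and no other section lifts it.

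The safety outcome is defined twice:

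- Section 14.2 lists "severity of adverse events; and change in vital signs and clinical laboratory results" as primary safety outcome measures.
- Section 9.5 lists "Incidence, nature, and severity of adverse events up to 1 week following antibody administration" and vital signs during administration, but not laboratory results.

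Section 17.3.2 requires CTCAE grading of all adverse events. On causality, Section 17.3.3 says: "The investigator will evaluate the potential relationship between all clinical AEs, abnormal laboratory values" and the tracer. Section 14.2 also calls for committee review before accrual continues: "If severe adverse effect (grade 3 or 4 CTCAE) is observed in any cohort".

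**The concern.** An unscheduled test ordered for an adverse event is done because something already looks wrong. Leaving such results out of the trial data makes missingness depend on the outcome being measured. A laboratory summary built only on the scheduled draws would tend to miss the worst value of an abnormality and would often not show whether it resolved.

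This matters because safety is a primary objective and Section 3.2.2 says that the intact antibody had not been used in humans. Laboratory change is a natural place to look: Table 3 projects 16.3 rad to red marrow from 5 mCi of the tracer, the second-highest organ dose in the table.

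**Working it through.** The plan states no figure on this point, so there is none to reproduce. The check sets the recording rule beside the laboratory schedule and the other recording routes.

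**Step 1. Scheduled post-dose laboratory sets per patient (Table 2 and footnotes).**

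- Cohort 1: footnote c gives a set at Days 6 to 8. The table as it reads here marks 4 to 6 weeks instead. That is one set if only one of the two applies and two if both do. The table layout may have suffered in text extraction, so both counts are carried forward.
- Cohort 2: one set, on the scan day, which is still to be determined.

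If every cohort fills, there are 6 + 6 + 15 = 27 patients. The scheduled post-dose sets then number between 12 × 1 + 15 × 1 = 27 and 12 × 2 + 15 × 1 = 39 for the whole study.

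**Step 2. What those sets can show.** One post-dose value gives a change from baseline. It cannot separate rise, peak and recovery. With two sets in Cohort 1, the first falls at 120–168 hours (Section 9.3), which is 5–7 days after injection, and the second at 4–6 weeks, which is 28–42 days. The gap is at least 28 − 7 = 21 days. Section 14.2 expects patients to start new therapy within about 2 weeks, so the later draw will often reflect that therapy too. In practice most patients have one scheduled draw that can be read as tracer safety.

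**Step 3. What the rule removes.** As an assumed illustration, suppose a value becomes abnormal on Day 3, is repeated on Day 4 because of an adverse event, and is back near baseline at the Day 7 draw. All three dates lie inside the one-week window of Section 9.5. Under Section 10.0 the CRF laboratory data hold only the Day 7 value.

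**Step 4. Whether another route restores the values.**

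- Sections 17.3.2 and 17.3.3 capture the event, its grade and its attribution. They do not put the result and its date into the CRF.
- Section 17.3 (SAE reporting) covers serious events through separate reports.
- Section 16.1 keeps source documents, so the values can be retrieved, but no planned step transcribes them.

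**Step 5. Use of serial values.** Section 17.3.3 classes a baseline abnormality as unrelated if its severity and frequency stayed the same, or if it is plainly due to the disease. Section 6.3 excludes AST/ALT only above 2.5 × ULN and platelets only below 75K/mcL, so patients can enter with mild abnormalities. The investigator can assess change from the medical record, but the CRF laboratory data may not show the basis.

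**The case against.** The strongest reply is that nothing important is lost. The investigator who orders a repeat test sees the result, must grade any adverse event and must assess abnormal laboratory values for causality, with no restriction to scheduled tests. Serious events are reported separately and source records remain. This largely stands for the adverse event data. It does not restore the laboratory outcome, because the instruction is not to transcribe the values.

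Two stronger readings are tempting, and the documents support neither.

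- A reader might infer that a hidden severe value would alter the toxicity condition for opening Cohort 1B or the accrual review, for example by turning 0/6 into 1/6 (16.7%), or 0/27 into 1/27 (3.7%) overall. Section 14.2 acts on toxicity that patients experience or that is observed, not on CRF laboratory entries. Neither shift is shown.
- A reader might point to a late abnormality, say on Day 10, that the CRF would miss. That date is outside the one-week window of Section 9.5 and the 6–8 day query period of Section 16.3. It may also follow the start of the drug conjugate, which Section 6.2 holds back only until imaging ends at about 1 week, or another new therapy.

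Three further points limit the concern. The excluded tests include some for treatment planning, which need not be abnormal. Section 14.2 expects few adverse events. It also specifies descriptive summaries for adverse events but no method for laboratory values, and Section 9.5 omits them, so the standing of the laboratory outcome is itself unsettled.

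**Conclusion.** The concern holds in a limited form. As written, the plan keeps event-driven laboratory results out of the CRF while Section 14.2 makes laboratory change a primary safety outcome. With one or two scheduled post-dose draws per patient, the summary can miss peak, time course and recovery, and may look milder than what occurred.

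The size cannot be given, because the documents state no frequency for unscheduled tests and no expected rate of laboratory abnormality. The conclusion assumes that Section 14.2 governs the outcome list and that tests prompted by an adverse event are more often abnormal than scheduled ones. The second is a reasonable inference, not a documented figure. Loss of adverse event counts or a changed cohort decision is not established. The correction is worth making because the results already exist and recording them costs little.

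**What to change.** 1. Delete the sentence in Section 10.0, or limit it to tests unrelated to adverse events.
2. Enter every unscheduled laboratory result obtained to investigate or follow up an adverse event in the CRF, with date and CTCAE grade.
3. In Section 14.2, report change at the scheduled draws and, beside it, the worst post-dose grade per patient over scheduled and unscheduled results. Restrict the latter to the stated safety window and to values before any new therapy starts. List later values separately with the date of new therapy.
4. Reconcile Sections 9.5 and 14.2 on whether laboratory change is a primary safety outcome, and make Table 2 and footnote c agree on the Cohort 1 post-dose draw.

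The cost is a short protocol edit, an unscheduled-laboratory CRF page and a little more data entry. No additional blood tests are needed. The laboratory table may look less favourable. A worst grade also tends to rise with the number of tests done, which is why change at the scheduled draws should stay beside it.

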Images will be analyzed with ROI and SUVmean and max measurements will be obtained. The serial quantitative data obtained over the various organs of interest (heart, liver, spleen, kidney, lung and any other organ that exhibits uptake will be collected. These data can then be utilized to determine organ time activity curves and the dosimetry can be calculated. Uptake and clearance values will be summarized using descriptive statistics (mean, median standard deviation. Once the biodistribution and pharmacokinetics have been characterized, subsequent patients will not require serial imaging and pharmacokinetics, but rather will have a single scan at an optimal time point determined based on the patients in cohort 1A and or cohort 1B. We will determine the time at which the greatest number of lesions are seen. This is likely to be between 3-8 days, but choice will be based on the first Cohort 1 patients' data, using the most frequent day at which the most lesions are seen and/or at times at which best contrast is observed determined visually. Thus, for the remainder of the patients in Cohort 2, PET scan will be performed once. The timing of this scan will be determined based on findings from Cohort 1A and/or 1B, as described above.

Infusion reactions with MSTP2109A intact IgG have not been evaluated. Infusion reaction to the ADC DSTP3086S antibody drug conjugate in 18 patient treated thus far have been minor and not clinically significant (i.e. none or Gr1). In the event of fever, rigors, shortness of breath, or other evidence of infusion reaction, patients may receive diphenhydramine 25-50 mg IV and Tylenol 650 mg PO as felt to be clinically appropriate by the treating physician. The emission data are typically acquired for 3–10 minutes per bed position depending upon the time post-injection and visual quality of the images. Index lesions will be identified based on the patient's conventional diagnostic imaging.

Images will be stored as Digital Imaging and Communications in Medicine (DICOM) on the PACS and HERMES. Images to be sent out to Genentech will be burned on a CD or equivalent by patient. All images will be anonymized according to institutional policy with the patients code used as identifiers.

No decision on the patients' health care management will be made on the basis of Imaging with ⁸⁹Zr-DFO-MSTP2109A.

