11.0 TOXICITIES/SIDE EFFECTS

Risks

⁸⁹Zr-DFO-MSTP2109A PET/CT Scans

As part of this scan there is radiation delivered from the ⁸⁹Zr and from the low dose CT scan that are performed as part of the CT for attenuation correction and co-registration. Although any exposure to ionizing radiation has the potential to cause some harm to tissue, the radiation exposures in this study are comparable to the low-level exposures associated with common diagnostic procedures such as CT scanning. There remains a low theoretical risk of developing a cancer at some point later in life as a result of the radiation exposure received in this study. This risk is particularly low for adults given the fact that the radiation from the scans will be over several weeks. Participants should not father a baby while on this study. Acceptable birth control methods include abstinence, double barrier method, surgically sterilized patient or partner. This risk is much smaller than the clinical risks posed by the patient's current cancer.

DFO-MSTP2109A

Potential risks associated with DFO-MSTP2109A are similar to those of other humanized antibody and include allergic reactions, characterized by fever, chills, and sometimes rashes or hives. Less likely shortness of breath can occur. Rare allergic reactions can present as shock or death or swelling of the throat. Such reactions are usually addressed by stopping the administration of the drug, administering steroids, acetaminophen and/or diphenhydramine, and restarting the drug at a slower rate if the reaction is not severe.

There is a very small risk of infection. This could cause itching or redness at the area on the patient's arm where the IV was placed.

Radiation Dosimetry

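### The listed vital signs leave out temperature and any respiratory measure, although fever and shortness of breath are named infusion reactions, so the vital-sign safety outcome cannot show either directly

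*Combined protocol and SAP*

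**What the plan says.** Section 10.0, under Vital Signs, consists of one sentence: "Blood pressure and heart rate will be obtained at the time points outlined in the flowchart". The Table 2 footnotes for both cohort schedules time the readings before infusion and then every 30 minutes for at least 2 hours. Section 16.3 repeats the half-hourly schedule and adds no further sign. Temperature, respiratory rate and oxygen saturation are not scheduled anywhere.

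Two sections describe the reactions to look for. Section 9.3 opens its instruction on reactions with "In the event of fever, rigors, shortness of breath, or other evidence of infusion reaction". Section 11.0 says the potential risks "include allergic reactions, characterized by fever, chills, and sometimes rashes or hives", then adds "Less likely shortness of breath can occur". It goes on to list shock, death and swelling of the throat as rare presentations.

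The safety outcomes appear twice. Section 9.5 lists "Incidence, nature, and severity of adverse events up to 1 week following antibody administration" and "Change in vital signs during administration". Section 14.2 again lists adverse events and adds "change in vital signs and clinical laboratory results", this time with no limit to the period of administration.

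**The concern.** Both lists of reactions begin with fever, and both include shortness of breath. The protocol makes vital-sign change a primary safety outcome but leaves out the sign that measures fever and any sign that measures breathing. Safety and tolerability are a primary objective. Section 3.2.2 says the intact antibody has not been used in humans, and Section 9.3 says infusion reactions to it have not been evaluated. This trial will therefore be the first source of such data.

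What is at stake is how completely and objectively two named reactions are ascertained. A rise in temperature that the patient does not notice would leave no trace. If a patient does feel hot or breathless, staff can take a reading, but there is no planned pre-infusion value to show whether it has changed. The final safety report could then state that vital signs did not change when the signs bearing on these two reactions were never taken.

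**Working it through.** The plan gives no figure to reproduce. The check sets the named reactions against the listed measurements, then the outcome window against the reading schedule.

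**Step 1. Named reactions against listed vital signs**

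| Reaction named | Where | Reflected in blood pressure or heart rate? | Other planned capture |
|---|---|---|---|
| Fever | 9.3, 11.0 | Not directly | Symptom or adverse-event report |
| Chills or rigors | 9.3, 11.0 | Not directly | Observation or adverse-event report |
| Shortness of breath | 9.3, 11.0 | Not directly | Symptom or adverse-event report |
| Rash or hives | 11.0 | No; not a vital sign on any usual list | Observation or adverse-event report |
| Throat swelling | 11.0 | No; not a vital sign on any usual list | Observation or adverse-event report |
| Shock | 11.0 | Yes | Also an adverse event |
| Hypotension (Grade 1 with the related drug conjugate) | 3.2.2 | Yes | Also an adverse event |

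The outcome is therefore informative for the haemodynamic presentations. Among the rest, fever and shortness of breath are the two for which an ordinary vital sign exists and is not scheduled. Chills, rash and throat swelling would stay with observation and adverse-event reporting whatever signs were listed.

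**Step 2. Extent**

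- Patients: up to 6 (Cohort 1A) + 6 (Cohort 1B, if opened) + 15 (Cohort 2) = 27.
- Infusion-day readings per patient: 1 before infusion + 120/30 = 4 over the minimum 2 hours, so at least 5.
- At each reading two signs are taken, and neither is temperature or a respiratory measure.

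**Step 3. Is there another pre-infusion comparator?**

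The Section 10.0 physical examination covers general appearance and lungs, and height and weight are recorded at baseline. Table 2 places this examination at screening, within 4 weeks before study entry. No temperature or respiratory rate is specified for it. It is not a reading taken just before infusion.

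**Step 4. The outcome window against the schedule**

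- Section 9.3: the infusion lasts 5 to 15 minutes.
- Table 2 footnotes: readings before infusion, then every 30 minutes.
- If the 30 minutes run from the start of infusion, the first later reading falls 30 − 15 = 15 to 30 − 5 = 25 minutes after the infusion ends.
- If they run from the end of infusion, it falls 30 minutes after the end.
- If they run from the pre-infusion reading, a reading could fall within the infusion only by chance.

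So no reading is guaranteed inside the window that Section 9.5 uses to define the outcome. Section 14.2 has no such window, and under its wording the scheduled readings do serve the outcome. The two sections must be reconciled.

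**The case against.** The strongest reply is that the vital-sign outcome does not stand alone. It sits beside adverse events, which can record every reaction named. Section 9.5 has patients monitored during and after infusion, Section 16.3 has them observed closely and queried for up to 6–8 days, and Table 2 schedules adverse-event collection on Day 1 and later imaging days. Rigors and breathlessness are seen or reported. Nothing prevents staff from taking a temperature when they suspect a reaction. The human data available are reassuring: Section 9.3 reports that reactions to the drug conjugate in 18 patients were absent or Grade 1.

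Much of this stands. A reader might infer that the vital-sign outcome cannot show the reactions it is meant to detect. The documents do not support that. No section ties the outcome to fever or breathlessness in particular, and blood pressure and heart rate do reflect shock, the gravest haemodynamic presentation named, as well as the hypotension seen with the conjugate. A reader might also infer that events could not be graded without these readings. That would rest on grading definitions the documents do not contain. In addition, Table 1 is organised around symptoms and gives the same guidance for Grades 1 and 2.

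The reply does not close the gap in planned measurement. Adverse-event capture of a fever needs a complaint or an unscheduled check. It supplies neither a systematic reading nor a pre-infusion value, and it does not make the separate vital-sign outcome informative about temperature or breathing.

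**Conclusion.** The point holds in a limited form. The listed vital signs omit temperature and any respiratory measure although fever and shortness of breath are named reactions. The vital-sign outcome can reflect shock or hypotension but cannot directly show these two. They depend on symptom and adverse-event reporting, without a scheduled reading or a pre-infusion comparator.

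The gap applies to all planned patients, but its effect on the results cannot be quantified. The documents give no rate of fever and no probability that one would go unreported. A reader might express one missed fever as a share of the six-patient cohort, but that would assume both that the event occurs and that it goes uncounted. The part most exposed is a temperature rise without symptoms, and the missing comparator when symptoms do occur.

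The conclusion assumes that the Section 10.0 sentence is the complete list of vital signs. If departmental practice already includes temperature and respiratory rate, the remaining fault is that the protocol does not say so or make them part of the outcome. This is an inexpensive improvement in safety ascertainment and does not make the trial unsound.

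**What to change.** In Section 10.0, list the vital signs as blood pressure, heart rate, temperature and respiratory rate, taken at the infusion-day time points already in the Table 2 footnotes. In Section 14.2, state that the vital-sign safety outcome is the change from the pre-infusion value, summarised for each sign.

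Reconcile the outcome window between Sections 9.5 and 14.2, so that the window named is one in which the scheduled readings fall.

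The cost is a line of text, two case report form fields and roughly a minute more per reading, or about 5 minutes per patient over the minimum five infusion-day readings. Vital signs are already being taken at these times, so no extra visit or staff is needed. The change concerns measurement and reporting only. No change to the management of reactions is proposed.
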